3.9 Changes to protocol-defined analyses

In the clinical study protocol the definition of the FAS included all subjects with a valid measurement of the primary efficacy variable post-Baseline. However, this was adjusted to all subjects with a valid Baseline measurement for the primary efficacy variable in the SAP in order to comply with program standards and FDA requirements (ie, inclusion into the FAS is no longer dependent on availability of post-Baseline data).

According to the final clinical study protocol spaghetti plots of change from Baseline in PASI would be plotted for each subject over time. However as the PASI response is based on percentage change, it was deemed more appropriate to present the individual plots based on percentage change from Baseline.

The protocol stated that exposure at risk for defining treatment-emergence for treatment-emergent adverse events (TEAEs) would be cut off at the Week 16 visit (for subjects who complete through the Week 16 visit) or at 20 weeks (140 days) after the last administration of study treatment (for subjects that discontinue prior to the Week 16 visit). This was further stated to be done in order to provide a fair comparison across all subjects when comparing the incidence of TEAEs. In this SAP amendment it has been clarified that the definition of a TEAE is any AE with onset following the first administration of study medication until the final administration of study medication + 140 days (regardless of study discontinuation). In order to allow for direct comparison of the treatment groups with respect to incidence of TEAEs, prior to the point at which subjects are eligible to enter the extension study, it would be necessary to use a cut off at Week 20 (ie, the first point at which a subject may enter the extension study). This has also been clarified in the SAP amendment accordingly.

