11.2 Adverse events

11.2.1 Definitions and classification of adverse events

All AEs will be recorded in the CRF from informed consent until study completion or termination.

Adverse events with start date prior to the first administration of IMP are defined as pre-treatment AEs. A TEAE is defined as any AE with a start date/time at the time of or after the first administration of IMP up until the last received dose of IMP + 140 days (which covers the 20 week SFU Period). Adverse events occurring after this date will not be classified as TEAEs and will therefore be excluded from the summary tables.

Where dates are missing or partially missing, AEs will be assumed to be treatment-emergent, unless there is clear evidence to suggest that the AE started prior to dosing. Handling of missing dates/times for classification of AEs as TEAEs is described in Section 4.2.4.

In order to allow for a comparative period across all subjects, prior to the point at which subjects are eligible to enter the extension study, TEAEs will be classified as follows:

- **Treatment Period TEAEs:** all TEAEs with onset at the time of or after the first administration of IMP up until the Week 20 visit. Any TEAEs that occur on the date of the Week 20 visit will be included (ie, the cut off will be assumed to be at 23:59 hours on the date of Week 20). Such TEAEs will be designated as 'Treatment Period' TEAEs in the tabulations. Any subjects that withdraw prior to Week 20 will have Treatment Period TEAEs cut off at 140 days relative to the first dose (ie, equivalent to 20 weeks).
- **Post-Treatment Period TEAEs:** all TEAEs with onset after the Week 20 visit up until the last dose of IMP + 140 days will be designated as 'Post-Treatment' TEAEs in the tabulations. Thus, any tabulation including Post-Treatment TEAEs will include only those TEAEs for subjects not entering the extension study at all or those TEAEs for subjects who enter the extension study at a later visit. For subjects that withdraw prior to Week 20, Post-Treatment Period TEAEs are classified as those starting after 140 days relative to the first dose (ie, equivalent to 20 weeks).

For the EAIR and EAER tabulations the above classifications will not be applicable, as these summaries are, by definition, adjusted for the individual exposure at risk for each subject.

All AEs will be coded and categorized by intensity (mild/moderate/severe) and relationship to IMP (related/not related).

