11.2.3 Presentation of adverse events

An overview of the number and percentage of subjects who experience TEAEs will be presented by treatment group (including All Subjects), based on the SS. This tabulation will include the number and percentage of subjects with any TEAEs, serious TEAEs, related TEAEs, discontinuation due to TEAEs, severe TEAEs, AEs leading to death and TEAEs leading to death; event counts will also be included. The tabulation will be repeated for Treatment Period TEAEs and Overall TEAEs.

In addition, the following summaries will be presented by treatment group (including All Subjects), SOC, high level term (HLT) and PT, based on the SS:

- Incidence of TEAEs during Treatment Period
- Incidence of TEAEs Overall
- Incidence of serious TEAEs during Treatment Period
- Incidence of serious TEAEs Overall

-
- Incidence of non-serious TEAEs during Treatment Period
 - Incidence of non-serious TEAEs Overall
 - Incidence of TEAEs during Treatment Period by relationship
 - Incidence of TEAEs Overall by relationship
 - Incidence of TEAEs during Treatment Period by maximum relationship
 - Incidence of TEAEs Overall by maximum relationship
 - Incidence of TEAEs during Treatment Period by maximum intensity
 - Incidence of TEAEs Overall by maximum intensity
 - Incidence of fatal TEAEs during Treatment Period by relationship
 - Incidence of fatal TEAEs Overall by relationship
 - Incidence of non-serious TEAEs during Treatment Period by relationship
 - Incidence of non-serious TEAEs Overall by relationship
 - Incidence of serious TEAEs during Treatment Period by relationship
 - Incidence of serious TEAEs Overall by relationship
 - Incidence of non-serious TEAEs during Treatment Period above threshold of 5% of subjects
 - Incidence of non-serious TEAEs Overall above threshold of 5% of subjects
 - Incidence of non-serious TEAEs during Treatment Period above threshold of 5% of subjects by relationship
 - Incidence of non-serious TEAEs Overall above threshold of 5% of subjects by relationship
 - Incidence of TEAEs during Treatment Period by SOC and PT (including the number and percentage of subjects and individual subject numbers/reported terms for each PT stratified by intensity, relationship and seriousness)
 - Incidence of TEAEs (including all TEAEs during Treatment and Post-Treatment Periods) by SOC, HLT and PT and including the EAIR and EAER calculated as described in [Section 11.2.2](#)

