11.3 Clinical laboratory evaluations

Laboratory data (clinical chemistry, hematology, and urinalysis) and changes from Baseline (if applicable) for numeric variables will be listed by treatment group and visit. Any laboratory variables with values that are BLQ or ALQ will be handled as described in [Section 4.2.2](#) for calculation of changes from Baseline and for summary tables. Values outside the reference range for the numeric variables will be flagged in the listings and in addition, will be listed separately. The reference ranges will also be reported in the listings.

Clinical chemistry and hematology variables will be summarized by treatment group (including All Subjects) at each visit, for both absolute values and changes from Baseline.

Laboratory variables will be grouped according to the laboratory function panel and categorized as normal, high or low, if applicable, based on the reference range supplied by the analytical laboratory. For selected variables that are identified in [Table 11-1](#), the change in category from Baseline will be presented in shift tables at all post-Baseline visits.

The number and percentage of subjects with treatment-emergent markedly abnormal (TEMA) laboratory results (to match the TEAE definition stated in [Section 11.1.3](#)) will be tabulated by treatment group and visit. Markedly abnormal laboratory values will be defined as those categorized as Grade 3 and above based on the ranges defined as per the Common Terminology Criteria for Adverse Events (CTCAE) Version 4.03 (2016). These are provided in [Table 14-4](#). The tabulation will include a category for the incidence of TEMA results over all visits which will also count unscheduled measurements.

In addition, for absolute neutrophil count (ANC), all grade 2 CTCAE abnormalities ($<1.5 - 1.0 \times 10^9/L$) will be listed separately, with results from all visits for any subject that has any grade 2 abnormality.

Laboratory measurements meeting the criteria for TEMA will be listed separately for hematology and chemistry. The listings will include all measurements for any variable with at least one TEMA result for each subject.

Any additional laboratory variables not included in the outputs described previously will be listed separately. These will include the following:

- Serology
- Pregnancy tests (serum and urine)
- Follicle stimulating hormone (FSH) (only for postmenopausal women)

The results of the Quantiferon TB Gold test will be listed separately.

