Subjects with treatment-emergent liver function test abnormalities at any post-Baseline visit will be summarized (number and percentage of subjects) by treatment group. The criteria for this tabulation are presented in [Section 14.5](#).

Table 11–1: Clinical laboratory measurements

Category	Panel	Variable
Serology	Serology	HIV1-Ab, HIV2-Ab, HBsAg, anti-HBc, anti-HBs, anti-HCV-Ab, TB
Hematology	Red blood cell	RBC count ^a , hemoglobin, hematocrit
	Red blood cell indices	MCH, MCHC, MCV
	Platelet	Platelets
	White blood cell	WBC count ^a
	White blood cell differential	Absolute counts: ANC ^a , basophils, eosinophils, ALC, monocytes, atypical lymphocytes (if indicated) Percentages: neutrophils/leukocytes, basophils/leukocytes, eosinophils/leukocytes, lymphocytes/leukocytes, monocytes/leukocytes.
Chemistry	Electrolytes	Sodium, chloride, potassium, calcium, magnesium
	Kidney function	BUN, creatinine
	Liver function	AST ^a , ALT ^a , GGT ^a , ALP ^a , LDH ^a , total bilirubin (direct bilirubin, indirect bilirubin, if indicated)
	Lipids	Total cholesterol ^a
	Metabolic function	Glucose
	Hormones	FSH ^b
	Fertility	Pregnancy test ^c
	Other	CRP
Urinalysis	Dipstick	pH, protein, blood, leukocyte esterase, nitrite, glucose

Table 11–1: Clinical laboratory measurements

Category	Panel	Variable
	Urine sediment (if indicated)	WBC, RBC, epithelial cells (squamous, transitional and renal tubular), hyaline casts, WBC casts, RBC casts, waxy casts, granular casts, calcium oxalate crystals, uric acid crystals, triphosphate crystals, yeast, bacteria, amorphous urates, amorphous phosphates

ALC=absolute lymphocyte count; ALP=alkaline phosphatase; ALT=alanine aminotransferase; ANC=absolute neutrophil count; AST=aspartate aminotransferase; BUN=blood urea nitrogen; CRP=C-reactive protein; FSH=follicle stimulating hormone; GGT=gamma glutamyltransferase; anti-HBc= hepatitis B core antibody; anti-HBs=hepatitis B surface antibody; HbsAg=hepatitis B surface antigen; HCV-Ab=hepatitis C virus antibody; HIV1-Ab=human immunodeficiency virus 1 antibody; HIV2-Ab= human immunodeficiency virus 1 antibody; LDH=lactate dehydrogenase; MCH=mean cell hemoglobin; MCHC=mean cell hemoglobin concentration; MCV=mean cell volume; RBC=red blood cell; TB=tuberculosis; WBC=white blood cell.

^a Shift tables will be presented for these variables.

^b FSH performed on postmenopausal females who have been postmenopausal for ≥ 1 year and last menstrual cycle occurred < 2 years ago.

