11.4 Vital signs, physical findings, and other observations related to safety

11.4.1 Vital signs

The following vital signs measurements will be obtained:

- Pulse rate
- Systolic and diastolic blood pressure
- Temperature (oral or otic)

A by-subject listing of all vital sign measurements and changes from Baseline will be presented by treatment group and visit. The listing will include a flag for measurements identified as TEMA/potentially clinically significant (PCS) as calculated by the criteria outlined in [Table 14–6](#).

Descriptive statistics will be reported for all vital sign measurements. Measured values and changes from Baseline will be summarized by vital signs variable and visit for each treatment group.

The number and percentage of subjects with TEMA/PCS vital sign values (to match the TEAE definition stated in [Section 11.1.3](#)) will be summarized by treatment group (including All Subjects) and variable at each visit and overall (ie, across all post-Baseline visits).

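### Minor: the cumulative liver, laboratory and blood-pressure tables lack the Week 20 cut-off that the SAP uses for adverse events, so the arms may be compared on unequal numbers of measurements

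*SAP*

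**What the plan says.** SAP 3.9 explains that to compare the arms directly on TEAE incidence before extension entry "it would be necessary to use a cut off at Week 20". SAP 11.2.1 carries this out by defining Treatment Period TEAEs as "all TEAEs with onset at the time of or after the first administration of IMP up until the Week 20 visit". For subjects who withdraw before Week 20 the period ends at 140 days from first dose. SAP 6.5.4 uses the same limit for concomitant medications.

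Three cumulative safety summaries by arm do not use it:

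- Liver abnormalities, Table 14-5 criteria (SAP 11.3): "Subjects with treatment-emergent liver function test abnormalities at any post-Baseline visit will be summarized (number and percentage of subjects) by treatment group".
- Laboratory TEMA results (SAP 11.3): "The tabulation will include a category for the incidence of TEMA results over all visits which will also count unscheduled measurements".
- TEMA/PCS vital signs, for which Table 14-6 has blood-pressure criteria only (SAP 11.4.1): by "variable at each visit and overall (ie, across all post-Baseline visits").

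SAP 11.3 and 11.4.1 say that TEMA should match the TEAE definition in Section 11.1.3. That section defines time at risk. The TEAE definition is in 11.2.1, and it runs to the last dose plus 140 days, so even the corrected reference would not bring in the Week 20 limit. The exposure-adjusted rates in SAP 11.2.2 are defined for TEAEs only. Under SAP 3.1 the default denominator is every subject in the analysis set and arm, however many measurements each had.

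**The concern.** A table that counts a subject once if any value qualifies depends on how often the subject was measured. SAP 2.3 lets previous PASI25 responders who relapse leave at Week 20, 24 or 28, while subjects not entering the extension continue to Week 36. Leaving depends on losing response around or after Week 16, and at Week 16 Arm A receives placebo and Arm B active drug. Number of measurements may therefore depend on regimen, and the arm with more exits, plausibly Arm A, would appear to have fewer abnormalities.

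Protocol 12.1.3 names liver enzyme changes and cytopenias for special monitoring, so readers will look at these tables by arm. The SAP identified this problem for adverse events and medications and solved it there, but did not carry the solution across.

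**Working it through.** **The plan's own figure.** 20 weeks × 7 = 140 days, as SAP 11.2.1 states. A last dose at Week 16 (day 112) plus 140 days is 252 days, or Week 36.

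**Scheduled measurements.** Protocol Table 5-1 and SAP 4.4 give post-Baseline visits at Weeks 2, 4, 8, 12, 16, 20, 24, 28 and 36, which is 9. Subjects leaving at Week 20, 24 or 28 have 6, 7 or 8. I treat the SFU assessments required before extension entry as part of the exit visit, not as an extra measurement.

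**Time at risk (SAP 11.1.3).** Followed to Week 36: 112 + 140 = 252 days. Leaving at Week 20: 140 + 1 = 141 days. A Week 20 leaver has 6/9 = 67% of the measurements and 141/252 = 56% of the time.

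**Effect on the crude percentage.** With a constant chance p of a qualifying value at each measurement, independent between visits and the same in both arms, the chance of at least one in L measurements is 1 − (1 − p)^L. The documents give neither p nor a relapse rate, so both are assumed.

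At p = 1%: L = 9 gives 8.65% and L = 6 gives 5.85%. With exits spread over Weeks 20/24/28:

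| Exits, Arm A (Wk 20/24/28) | Exits, Arm B (Wk 20/24/28) | Mean measurements, A v B | Any-visit %, A v B | Gap (points) |
|---|---|---|---|---|
| 0 | 0 | 9 v 9 | 8.65 v 8.65 | 0 |
| 5/5/10% | 5/5/10% | 8.65 v 8.65 | 8.32 v 8.32 | 0 |
| 5/5/10% | 0 | 8.65 v 9 | 8.32 v 8.65 | 0.3 |
| 10/15/15% | 0/0/5% | 8.25 v 8.95 | 7.95 v 8.60 | 0.65 |
| 20/20/20% | 0/5/5% | 7.80 v 8.85 | 7.53 v 8.51 | 1.0 |

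A harsher set puts every exit at Week 20 in one arm and none in the other:

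- p = 1%, 20% exits: 0.2 × (8.65 − 5.85) = 0.6 points.
- p = 3%, 40% exits: L = 9 gives 24.0% and L = 6 gives 16.7%; 0.4 × 16.7 + 0.6 × 24.0 = 21.1%, a gap of 2.9 points.
- p = 5%, 60% exits: 0.6 × (36.98 − 26.49) = 6.3 points.

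The bounding case, all of one arm leaving at Week 20 and none of the other, gives 2.8 points at p = 1% and 10.5 at p = 5%. Nothing in the documents suggests it.

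**Scale.** One subject is 1/30 = 3.3 points in Arm A and 1/15 = 6.7 points in Arm B.

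**With a Week 20 limit.** Every subject followed to Week 20 has 6 scheduled measurements in either arm, so the gap due to extension entry is 0 for any relapse rate.

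**The case against.** The case for leaving the plan alone is good on size and on context.

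- SAP 3.9 limits its reasoning to TEAE incidence. The study is descriptive, is not powered for safety (SAP 2.4), and has no between-arm safety test. This stands: the point is about consistency, not a breach of a stated rule.
- A reader might infer that an arm difference could never be separated from a difference in number of measurements. The documents do not support that. Laboratory TEMA and blood pressure are also tabulated by visit, so Weeks 2 to 20 can be compared visit by visit. AST, ALT, GGT and ALP also have shift tables at every post-Baseline visit. Two limits remain: by-visit rows cannot be added up to a subject-level incidence, and for liver tests they use Grade 3 limits (Table 14-4) or the reference range, not the Table 14-5 thresholds or the combined bilirubin and transaminase criteria.
- Liver events and cytopenias have special-monitoring AE tables with EAIR and EAER (SAP 11.2.3, 14.6), and Protocol 12.5.1 requires all PDILI events to be reported as AEs. This stands.
- The higher assumed rates fit TEMA poorly. TEMA means Grade 3 or above, and Protocol 6.3, criterion 11, withdraws every subject with such a value. A cumulative 24% would be about 11 of 45 subjects. Rates of 3 to 5% per measurement are arguable only for the low-threshold liver rows.
- A reader might extend the point to the all-period AE tables, such as "Incidence of serious TEAEs Overall". That does not hold: SAP 11.2.3 plans a Treatment Period counterpart for that table and for the other Overall TEAE tables.
- A Week 20 row is a weak basis for comparing regimens. Week 16 assessments are predose (Protocol 8.7), so five of its six scheduled measurements precede the only treatment difference. This stands and shapes the fix.

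**Conclusion.** The gap is real but minor. The three cumulative summaries have neither the common period that the SAP uses elsewhere nor an exposure adjustment, and 6 v 9 scheduled measurements can arise from regimen-dependent exit. If exits differ by arm, the crude percentages favour the arm with more exits.

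At an assumed 1 to 5% per measurement and 20 to 60% exits in the arm with more exits, the spurious gap is about 0.3 to 6 points. That is less than one subject in Arm B and at most about two in Arm A (6.3/3.3 = 1.9). It is zero if exits are equal. The size rests on assumed exit and abnormality rates and on a constant, independent chance per visit; the counts of 6 and 9 do not. The liver table matters most, because it has no by-visit version at its own thresholds.

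A reader might go further and infer that a liver or cytopenia signal would be hidden, or that a Week 20 row alone would settle the arm comparison. The documents support neither.

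**What to change.** In SAP 11.3 and 11.4.1, for the three cumulative summaries and the liver table first:

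- Add a row for the Treatment Period through the Week 20 visit, using the 11.2.1 limit (for earlier withdrawals, "cut off at 140 days relative to the first dose (ie, equivalent to 20 weeks")). State whether unscheduled values count in it, since the laboratory TEMA all-visits category includes them.
- For the all-visits row, add a first-abnormality rate per 100 subject-years using equation [13], with time running from first dose to the first qualifying value, or to the end of time at risk if there is none.
- Keep the crude all-visits row as descriptive, and state that its percentages should not be compared between arms.
- Correct the cross-reference for the TEAE definition from 11.1.3 to 11.2.1.

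The cost is a few sentences and slightly longer tables, from data already collected. Neither addition is sufficient alone. The Week 20 row holds one scheduled measurement after the regimens diverge and omits later abnormalities. The rate adjusts for time, not for number of measurements, and the two do not match exactly (56% v 67% for a Week 20 leaver). The two should be read together.

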11.4 Vital signs, physical findings, and other observations related to safety

11.4.1 Vital signs

The following vital signs measurements will be obtained:

- Pulse rate
- Systolic and diastolic blood pressure
- Temperature (oral or otic)

A by-subject listing of all vital sign measurements and changes from Baseline will be presented by treatment group and visit. The listing will include a flag for measurements identified as TEMA/potentially clinically significant (PCS) as calculated by the criteria outlined in [Table 14–6](#).

Descriptive statistics will be reported for all vital sign measurements. Measured values and changes from Baseline will be summarized by vital signs variable and visit for each treatment group.

The number and percentage of subjects with TEMA/PCS vital sign values (to match the TEAE definition stated in [Section 11.1.3](#)) will be summarized by treatment group (including All Subjects) and variable at each visit and overall (ie, across all post-Baseline visits).

11.4.2 Body weight

A by-subject listing of body weight will be presented, including changes from Baseline. No summary tabulations will be provided for this variable.

11.4.3 Electrocardiograms

Standard 12-lead ECG recordings will be obtained after 10 minutes of rest in the supine or semirecumbent position. The following ECG variables will be reported together with the Investigator's interpretation of the ECG profile:

- PR interval
- QRS interval
- QT interval
- Heart rate
- QT corrected for heart rate using Fridericia's formula (QTcF)

The results of all ECG variables will be reported in the by-subject listings. The listing will also include the change from Baseline and will be presented by treatment group and visit.

Measured values and changes from Baseline will be summarized for each variable by treatment group and visit.

The following cut-points in QTcF (raw data and change from Baseline) will be summarized categorically by treatment group (number and percentage of subjects) and visit. The denominator for the percentages will be the number of subjects with a non-missing measurement for the variable at the specific visit.

Raw QTcF data:

- <450msec
- ≥ 450 msec to <480msec
- ≥ 480 msec to <500msec
- ≥ 500 msec

Change from Baseline QTcF:

- <30msec
- ≥ 30 msec to <60msec
- ≥ 60 msec

Electrocardiogram findings will be listed separately.

